3.2.3 Study Interruption or Study Withdrawal

A patient may be taken off this study early or may discontinue participation in this clinical study due to the following factors:

- Serious or intolerable adverse reaction to treatment
- Progression of disease
- Protocol violation
- Withdrawal of consent
- Withdrawal of sponsor support

There is no limit to how long a patient can have their treatment on hold. Prolonged holds are not considered “serious or intolerable adverse reactions to treatment.”

3.2.4 Monitoring of everolimus suspected toxicities: Patients whose treatment is interrupted or permanently discontinued due to an adverse event or abnormal laboratory value suspected to be related to everolimus must be followed at least weekly until the adverse event or abnormal laboratory completely resolves or returns to baseline as clinically appropriate. For patients whose treatment is on hold, labs will be monitored every two weeks while on hold.

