3.2.5 Known Undesirable Side Effects of everolimus

Overall, safety data available from completed, controlled and uncontrolled studies indicate that everolimus is generally well tolerated at weekly or daily dose schedules. The safety profile is characterized by manageable adverse events (AEs). These AEs are generally reversible and non-cumulative.

Adverse events most frequently observed with everolimus are stomatitis, rash, diarrhea, fatigue, infections, asthenia, nausea, peripheral edema, decreased appetite, headache, dysgeusia, epistaxis, mucosal inflammation, pneumonitis, weight decreased, vomiting, pruritus, cough, dyspnea, dry skin, nail disorder, and pyrexia. Overall, the most frequently observed laboratory abnormalities include decreased hematologic parameters including hemoglobin, lymphocytes, platelets, and neutrophils (or collectively as pancytopenia); increased clinical chemistry parameters including cholesterol, triglycerides, glucose, aspartate transaminases, creatinine, alanine transaminases, and bilirubin; and decreased clinical chemistry parameters including phosphate and potassium. The majority of these AEs have been of mild to moderate severity (NCI CTC grade 1-2).

Everolimus has immunosuppressive properties and may predispose patients to bacterial, fungal, viral or protozoan infections, including infections with opportunistic pathogens. Localized and systemic infections, including pneumonia, other bacterial infections, invasive fungal infections, such as aspergillosis or candidiasis and viral infections including reactivation of hepatitis B virus, have been described in patients taking everolimus. Some of these infections have been severe (e.g. leading to sepsis, respiratory or hepatic failure) and occasionally have had a fatal outcome.

Physicians and patients should be aware of the increased risk of infection with everolimus. Treat pre-existing infections prior to starting treatment with everolimus. While taking everolimus, be vigilant for symptoms and signs of infection; if a diagnosis of infection is made, institute appropriate treatment promptly and consider interruption or discontinuation of everolimus. If a diagnosis of invasive systemic fungal infection is made, discontinue everolimus and treat with appropriate antifungal therapy.

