Because dose will be managed to target a therapeutic window, toxicity evaluation in this study will be based on events that would indicate either the therapeutic dose was too toxic to maintain or that this method increased the probability of unexpected complications. These events include any patient for which the minimum 2.5 mg everolimus every other day was not tolerable or any unexpected hospitalizations during protocol participation. We will monitor the study continuously. If it becomes evident that the proportion of failures convincingly exceeds 15%, the study will be halted for a safety consultation. The stopping rule will hold enrollment if the posterior probability of failure being larger than 0.15 is 75% or higher. The prior for this monitoring rule is beta(1, 6). This means that our prior guess at the proportion of failures is 14.3%, and there is 90% probability that this proportion is between 0.85% and 39%.

Stop if	2AEs	3AEs	4AEs	5AEs	6AEs	7AEs	8AEs	9AEs	10AEs	11AEs	12AEs
in N	2-5	6-11	12-16	17-22	23-28	29-34	35-40	41-46	47-52	53-58	59-60

The next table shows the percent of the time that the stopping rule will terminate the study under different hypothetical risks of AEs, along with the average sample size (based on 5000 simulations).

Risk of AE	0.05	0.10	0.15	0.20	0.25	0.30	0.35
% of Time Study Stops	3.2%	18.5%	49.7%	79.4%	95.2%	99.2%	99.9%
Expected Sample Size	58.3	51.2	38.6	25.4	16.1	10.9	8.0

Early Stopping Guideline for Futility and Simulation Sample Size:

This study will be monitored for efficacy as well as toxicity. If the study meets the accrual goal of 20 patients per year, accrual would be completed by the time the first patients enrolled on study reach the three year efficacy endpoint. We will therefore monitor the study based on one-year EFS, knowing that if the one-year EFS is convincingly less than our targeted EFS at three years, the study would not meet its efficacy objective and the trial should be halted. Patients that have not progressed or died will be censored at the last date they were assessed and deemed relapse-free.

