1-yr EFS	Prob Stop for Futility	Avg N	Est 1- yr PFS	Lo 95% Post Int'l	Hi 95% Post Int'l	Prob H0 Rejected
0.45	0.60	40.3	0.42	0.25	0.58	0.03
0.5	0.37	47.7	0.47	0.25	0.62	0.12
0.55	0.17	54.1	0.53	0.35	0.67	0.28
0.60	0.07	57.5	0.59	0.40	0.72	0.57
0.65	0.02	59.1	0.64	0.50	0.77	0.83
0.70	0.01	59.8	0.70	0.58	0.82	0.96

Analysis of primary objective:

The proportion of patients positive for the toxicity evaluation as defined for this study: patients for which the minimum 2.5 mg everolimus every other day was not tolerable or any unexpected hospitalizations during protocol participation will be reported with an exact binomial calculation and 95% confidence interval. The proportion of patients requiring dose adjustments down as well as the proportion requiring dose adjustments up will be reported separately with confidence intervals. All other grade 1 and 2 toxicities will be reported by type and grade, overall and within intervals throughout the study (0, 60], (60, 90], (90,120], (120, 180], (180, 365] and (365, 1460].

Analysis of secondary objectives:

Standard life table methods will be used to analyze EFS. We will report the one and three-year EFS with 95% confidence intervals. The three-year EFS will be compared to the null EFS of 49% with a Z-score and a one-sided alpha level of 0.05.

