Reference: Internal Clinical Pharmacology Drug-drug interaction (DDI) memo, updated Oct. 2, 2011, 29-Oct-2012 which summarizes DDI data from three sources including the FDA's "Guidance for Industry, Drug Interaction Studies", the University of Washington's Drug Interaction Database, and Indiana University School of Medicine's Drug Interaction Table.

Addendum 4: Dose Modifications for abnormal serum drug concentrations without grade III/IV toxicities, grade \geq III toxicities (CTCAE version 4.0) except for stomatitis and lipid/hyperglycemia toxicities

- Patient will have regularly scheduled everolimus levels drawn throughout the study
- Everolimus is available in 2.5mg, 5mg and 10mg strengths
- The reference range for patients experiencing a <II common toxicity (CTCAE version 4.0) is 3-15ng/mL
- Anytime a dose is adjusted, repeat everolimus serum trough levels will be re-drawn 14 days (\pm 3 days) later. As clinically possible, all patients' other labs will be reset to match this new everolimus serum trough level schedule.
- Once everolimus is held due to high serum trough levels, everolimus should be held for 7 days before restarting at a lower dose level.
- During a treatment hold, everolimus levels will not be drawn once the serum trough level is less than 1.0.
- There is no limit on how long a patient can be on everolimus treatment hold. Labs will be monitored every two weeks while the patient is on hold.
- For patients >15 ng/mL or <3.0 ng/mL and not experiencing >II grade common toxicity, their dose will be adjusted by $+/-.2.5$ mg/day; lowest dose allowed is 2.5mg every 4 days. The study nurse will provide a calendar to patients when the dose level is 2.5 mg taken every 3 or 4 days
- If a patient on a schedule of 2.5 mg (QOD) or lower misses a dose, that dose should be made up.
- Non-hematologic grade \geq III CTCAE toxicities: hold drug until CTCAE toxicity is (I) but can be continued at grade 2 if the baseline values were within the range of grade 2 and restart at a dose level -2.5mg/day. Lowest dose allowed is 2.5mg every 4 days
- Grade 4 or 4 clinical failure – discontinue RAD001
- Recurrence of grade 4 toxicity after dose reduction – discontinue RAD001
- Hematologic grade \geq III CTCAE toxicity
 - Anemia
 - Hgb <8.0 g/dL: transfuse RBC; hold drug for 7 days or until Hgb >10 mg/dL (untransfused): whichever is longer. Restart at a dose - 2.5mg/day. Lowest dose allowed is 2.5mg every 4 days
 - Thrombocytopenia

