Treatment of hyperlipidemia should take into account the pre-treatment status and dietary habits. Blood tests to monitor hyperlipidemia must be taken in the fasting state. Hyperlipidemia and hypertriglyceridemia should be treated according to local best clinical practice. Patients should be monitored clinically and through serum chemistry for the development of rhabdomyolysis and other adverse events as required in the product label/data sheets for HMG-CoA reductase inhibitors.

Management of hyperlipidemia and hyperglycemia

Adverse Drug Reaction	Severity	Afinitor Dose Adjustment and Management Recommendations
Metabolic events (e.g. hyperglycemia, dyslipidemia)	Grade 1	No dose adjustment required. Initiate appropriate medical therapy and monitor.
	Grade 2	No dose adjustment required. Manage with appropriate medical therapy and monitor.
	Grade 3	Temporary dose interruption. Re-initiate Afinitor at lower dose. Manage with appropriate medical therapy and monitor.
	Grade 4	Discontinue Afinitor and treat with appropriate medical therapy.

Dyslipidemia (including hypercholesterolemia and hypertriglyceridemia) has been reported in patients taking everolimus. Monitoring of blood cholesterol and triglycerides prior to the start of everolimus therapy and periodically thereafter as well as management with appropriate medical therapy is recommended.

Hyperglycemia has been reported in patients taking everolimus. Monitoring of fasting serum glucose is recommended prior to the start of everolimus therapy and periodically thereafter. More frequent monitoring is recommended when everolimus is co-administered with other drugs that may induce hyperglycemia. Optimal glycemic control should be achieved before starting trial therapy.

Addendum 7: Management of non-infectious pneumonitis

Non-infectious pneumonitis is a class effect of rapamycin derivatives. Cases of non-infectious pneumonitis (including interstitial lung disease) have also been described in patients taking everolimus. Some of these have been severe and on rare occasions, a fatal outcome was observed.

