Grade 2 (Symptomatic, not interfering with Activities of Daily Living)	CT scan with lung windows. Consider pulmonary function testing includes: spirometry, DLCO, and room air O ₂ saturation at rest. Consider a bronchoscopy with biopsy and/or BAL. Monitoring at each visit until return to \leq grade 1. Return to initial monitoring frequency if no recurrence.	Symptomatic only. Consider corticosteroids and/or other supportive therapy if symptoms are troublesome.	Rule out infection and consider interruption of Everolimus until symptoms improve to Grade \leq 1. Re-initiate Everolimus at one dose level lower. Discontinue Everolimus if failure to recover within \leq 28 days.
Grade 3 (Symptomatic, Interfering with Activities of Daily Living. O ₂ indicated)	CT scan with lung windows and pulmonary function testing includes: spirometry, DLCO, and room air O ₂ saturation at rest. Monitoring at each visit until return to \leq grade 1. Return to initial monitoring frequency if no recurrence. Bronchoscopy with biopsy and/or BAL is recommended.	Consider corticosteroids if infective origin is ruled out. Taper as medically indicated.	Rule out infection and interrupt Everolimus until symptoms improve to Grade \leq 1. Consider re-initiating Everolimus at one dose level lower (approximately 50% lower than the dose previously administered depending on individual clinical circumstances) Discontinue Everolimus if failure to recover within \leq 28 days. If toxicity recurs at Grade 3, consider discontinuation
Grade 4 (Life-threatening, ventilatory support indicated)	CT scan with lung windows and required pulmonary function testing, if possible, includes: spirometry, DLCO, and room air O ₂ saturation at rest. Monitoring at each visit until return to \leq grade 1. Return to initial monitoring frequency if no recurrence. Bronchoscopy with biopsy and/or BAL is recommended if possible.	Consider corticosteroids if infective origin is ruled out. Taper as medically indicated.	Rule out infection and discontinue Everolimus.

Addendum 8: Action to be taken for positive baseline hepatitis B results

Test	Result	Result	Result	Result	Result
HBV-DNA	+	+ or -	-	-	-
HBsAg	+ or -	+	-	-	-
HBsAb	+ or -	+ or -	+ and no prior HBV vaccination	+ or -	- or + with prior HBV vaccination
HBcAb	+ or -	+ or -	+ or -	+	-

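### As written, the primary safety failure omits a patient permanently taken off everolimus for toxicity above 2.5 mg every other day who is not unexpectedly hospitalized

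*Combined protocol and SAP*

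**What the plan says.** Section 6.0, under the analysis of the primary objective, defines the toxicity evaluation by two criteria: "patients for which the minimum 2.5 mg everolimus every other day was not tolerable or any unexpected hospitalizations during protocol participation". The early stopping guideline for safety in the same section uses the same pair, but introduces it less tightly: "These events include any patient for which the minimum 2.5 mg everolimus every other day was not tolerable or any unexpected hospitalizations". That guideline gives the purpose as capturing events which show that the therapeutic dose could not be sustained because of toxicity, or that the method caused unexpected complications.

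Elsewhere the protocol ends everolimus for toxicity without reference to the dose being taken:

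- Addendum 5 (grade 4 stomatitis) and Addendum 6 (grade 4 metabolic events): "Discontinue Afinitor and treat with appropriate medical therapy".
- Addendum 7, grade 4 pneumonitis: "Rule out infection and discontinue Everolimus". The grade 2 and grade 3 rows also call for discontinuation if the patient has not recovered within 28 days.
- Addendum 9: study drug is discontinued if hepatitis B reactivation takes more than 28 days to resolve.
- Section 3.2.5: "If a diagnosis of invasive systemic fungal infection is made, discontinue everolimus".
- Addendum 4: "Recurrence of grade 4 toxicity after dose reduction – discontinue RAD001".

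Section 3.2.3 also lists "Serious or intolerable adverse reaction to treatment" as a general reason for coming off study. No passage says that permanent discontinuation for toxicity is itself a failure.

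**The concern.** The first criterion tests one dose level. A patient stopped for toxicity at a higher dose, with no step down, has not been observed at that level, so non-tolerance of it cannot be shown. Without an unexpected admission the second criterion is not met either. Read literally, such a patient enters the primary proportion as a non-failure and adds nothing to the stopping count. A patient whose toxicity is handled by stepwise reduction can reach the tested level and be counted.

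Permanent discontinuation for toxicity is the most direct evidence that a dose could not be maintained. At stake are the primary estimate and the only formal safety stopping rule in an uncontrolled study. The rest of the analysis does not reliably recover the events. Sections 2.0 and 6.0 describe safety and sample size in terms of grade 3 or higher toxicity, but the analysis text plans no such proportion. It lists dose adjustments and the other grade 1 and 2 toxicities.

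**Working it through.** **Step 1. Which paths are left out?** Everolimus starts above 2.5 mg every other day under either stated starting dose (2.5 mg daily in Sections 3.3.1 and 6.0; 10 mg daily in calendar footnote 10, a conflict to be reconciled). So a patient can be stopped before reaching the tested level. Each path is set against the two criteria:

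| Path | Meets a criterion as written? |
|---|---|
| Grade 4 metabolic event, laboratory only (Addendum 6) | Neither, if managed as an outpatient |
| Grade 2 pneumonitis not recovered in 28 days (Addendum 7) | Neither, if managed as an outpatient |
| Hepatitis B reactivation not resolved in 28 days (Addendum 9) | Neither, if managed as an outpatient; the definition applies with or without symptoms |
| Grade 4 stomatitis; grade 3 or 4 pneumonitis; invasive fungal infection | Mostly yes, through hospitalization |
| Recurrent grade 4 after reduction (Addendum 4) | Often yes: a reduction from 2.5 mg daily is already to every other day or less |
| Neutropenia (Addendum 4) | Not a discontinuation path; held and restarted lower |

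**Step 2. Reproduce the stopping rule.** Inputs from Section 6.0: prior beta(1,6), limit 0.15, threshold 75%, maximum N 60. After s failures in n patients the posterior is Beta(1+s, 6+n−s). Enrolment is held if P(rate > 0.15) ≥ 0.75. Examples:

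- n = 5, s = 2: 0.779, hold.
- n = 6, s = 2: 0.736, continue.
- n = 6, s = 3: 0.908, hold.

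The boundary matches the printed table at every N from 2 to 60.

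Stopping probabilities come from the exact recursion f_n(s) = (1−p)·f_{n−1}(s) + p·f_{n−1}(s−1), removing the mass at or above the boundary after each patient:

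| Failure rate p | Printed | Exact |
|---|---|---|
| 0.05 | 3.2% | 3.5% |
| 0.10 | 18.5% | 19.2% |
| 0.15 | 49.7% | 50.2% |
| 0.20 | 79.4% | 80.0% |
| 0.25 | 95.2% | 94.9% |

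The rule is computed correctly. The gap is in what counts as an event.

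**Step 3. Anchor for the missed fraction.** Section 1.1.3 reports grade 4 hypertriglyceridemia in 1 of 37 patients: 1/37 = 2.7%, exact 95% interval 0.07% to 14%. That was at 10 mg daily in relapsed or refractory aggressive lymphoma. Applied to this trial it would be 60 × 1/37 = 1.6 patients. Nothing in the documents gives a rate for the other paths, or for outpatient management.

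**Step 4. Effect, with the missed fraction assumed.** Counted rate = true rate − missed rate. Take a true rate of 20%:

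| Missed | Counted rate | Chance of stopping |
|---|---|---|
| 0 points | 20% | 80.0% |
| 3 points | 17% | 63.5% |
| 5 points | 15% | 50.2% |

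At a true rate of 15% with 5 points missed, the counted rate is 10% and the chance of stopping falls from 50.2% to 19.2%.

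For the final estimate, 5 points is 3 of 60 patients. Twelve failures give 20% (exact 95% interval 10.8% to 32.3%). Nine give 15% (7.1% to 26.6%).

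**The case against.** Four arguments on the other side deserve weight.

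1. *The stopping guideline is open-ended.* It says the events include the two criteria, and its stated purpose would cover these patients. A patient removed for toxicity might also be said not to have tolerated even the minimum. This leaves room for the broader reading in the stopping guideline. The primary analysis text, however, gives the two criteria as the study's definition. Failing a higher dose does not imply failing a lower one, which is the premise of the dose-reduction scheme.

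2. *Most severe events bring an admission.* This stands. A reader might infer that every patient stopped at a higher dose escapes the endpoint. The documents do not support that. Addendum 5 describes grade 4 stomatitis as life-threatening, and Addendum 7 describes oxygen need at grade 3 pneumonitis and ventilatory support at grade 4. Recurrent grade 4 toxicity may already arise at or below every-other-day dosing. The hepatitis B path is also narrow, because surface-antigen-positive patients are excluded.

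3. *The overall bias is not established.* This stands too. The second criterion counts any unexpected hospitalization whatever its cause. The first counts patients who cannot tolerate every-other-day dosing but may continue at 2.5 mg every 4 days. Both add failures. It would be tempting to say that the endpoint as a whole favours the regimen; only the direction of this one omission is clear.

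4. *The events are still visible.* Grade 3 or higher and serious events are recorded and reviewed. That helps oversight but does not put them in the primary proportion or the stopping count.

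**Conclusion.** The point holds in limited form. As the primary analysis is written, a patient permanently taken off everolimus for toxicity above 2.5 mg every other day, and not unexpectedly hospitalized, meets neither failure criterion. The firm examples are laboratory grade 4 metabolic events and grade 2 pneumonitis or hepatitis B reactivation unresolved at 28 days. For these patients the omission can only lower the count of failures and the chance of a hold.

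The size is not known. The fall from 80% to about 64% or 50% rests on an assumed true rate of 20% and assumed losses of 3 or 5 points; about 3 points is the better anchored, and only loosely. A reader might reach a figure near 8% by adding the 2 of 37 grade 4 neutropenias in the same earlier study. That is not supported, because Addendum 4 holds and restarts everolimus for neutropenia. The 5% grade III/IV pulmonary toxicity quoted for temsirolimus does not measure this gap either: it is another drug, both grades are combined, and such cases would mostly be admitted.

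**What to change.** In both the early stopping guideline and the analysis of the primary objective in Section 6.0, add a third criterion in identical words: *or everolimus permanently discontinued for toxicity at any dose*. Count each patient once. Make the two lists the same and closed.

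Record the reason for discontinuation for qualifying grade 2 events as well. Section 3.4.4.1 collects adverse events of grade 3 or above, so unresolved grade 2 pneumonitis could go unrecorded. Hepatitis B reactivation is already recorded as at least grade 3 under Addendum 9.

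Cost: one sentence in two places and one data field. The reported failure rate and the chance of a hold rise slightly. The 15% limit and the beta(1,6) prior were set for the present two-part event, so the sponsor should confirm that they still apply. If they do, the boundary and the sample size of 60 stand.

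Separately, the endpoint calls 2.5 mg every other day the minimum, while the study design text in Section 6.0 and Addendum 4 allow 2.5 mg every 4 days. These passages must be reconciled. No change to any dose or discontinuation rule is proposed.

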The Sidney Kimmel Comprehensive Cancer center has pioneered the concept of high-dose cyclophosphamide without stem cell rescue for over a decade. This high-dose consolidative treatment was developed for two main reasons.

It does not require stem cell rescue: it eliminates the potential of cancer re-introduction at time of stem cell rescue. Moreover, as this high-dose therapy does not require stem cell rescue all the components of autologous stem cell transplant: collection, preservation and re-infusion are eliminated making this therapy a more widely available treatment modality.

Tolerability: not only are the majority of the patients treated with this modality served in the outpatient setting, many have had a performance status or advanced age not otherwise well suited for an autologous stem cell transplant.

We put forward that the cytoreduction achieved by high-dose consolidative cyclophosphamide represents the ideal foundation for the integration of novel molecularly targeted compounds for these lymphomas.

81 adults received, as outpatients, rituximab [375mg/m² days 1, 4, 8, 11, 45, 52] and cyclophosphamide [50mg/kg days 15-18 with concurrent mesna] and pegfilgrastim (day +20). Forty-two participants had low grade B cell lymphoma [grade I/II follicular (69%), transformed lymphoma (17%), other (15%)]: 45% were treated without measurable disease. Thirty-nine had mantle cell lymphoma: 82% were treated without measurable disease. All achieved hematopoietic recovery; 46% required brief hospitalizations. The EFS for low grade B cell patients at 3 and 5 years was 49% and 40% with an overall survival (OS) at 3 and 5 years of 86% and 72%. The 3 and 5 year EFS for MCL patients was 57% and 39% with a 3 and 5 year OS 92% and 62%.

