Hodgkin's data: Rituximab, high dose cy, and GM-CSF based immunotherapy for relapsed Hodgkin's lymphoma: This phase I/II, single-institution trial for relapsed classical Hodgkin lymphoma has just completed accrual of its planned 30 patients. Clinical outcomes of this platform, which was developed as a potentially less toxic alternative to autologous BMT, are encouraging. In the first 25 patients, whose median time between first-line therapy completion and relapse was 12 months, actuarial event-free survival is 79% at 1 year and 63% at 2 and 3 years following high-dose cyclophosphamide; overall survival is 100% at 2 years and 92% at 3 years. These early results are comparable to what is seen with autologous BMT. The toxicity profile has been manageable, and there has been no treatment-related mortality. Median time to neutrophil recovery after high dose cyclophosphamide was 17 days, and 21 days for platelet recovery with 5 patients not

requiring platelet transfusion. The trial was presented in a poster session at the 52nd American Society of Hematology annual meeting (Kasamon Y et al, *Blood* 2010, abstract 3954).

2.0 Primary Study Objective:

To determine the safety of maintenance rituximab and prolonged mTOR inhibition with everolimus in CD20+, B cell lymphomas, Gray Zone Lymphoma, and Hodgkin's Lymphoma after high-dose consolidative therapy.

- Safety will be determined by the extent of avoidance of \geq grade III common toxicities (CTCAE version 4.0)

2.1 Secondary Objectives:

- 1) The secondary endpoint of this study is to evaluate event free survival (EFS) at three years based on histology.
 - EFS will be histology grade specific: Mantle cell lymphoma group, low-grade lymphoma group, high-grade lymphoma group
- 2) To determine whether maintenance rituximab with everolimus treatment reduces the frequency of circulating cancer cells.
- 3) To determine if relapsed disease is sensitive, in-vivo, to mTor kinase inhibition.

3 Investigational plan

3.1 Overall study design: After high dose consolidative therapy, patient will receive one year of adjuvant rituximab and everolimus. Treatment evaluation with radiographs, standard laboratories and examination will follow for the next three years. Survival/disease status will also be assessed for an additional two years, for up to 5 years total of follow-up.

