The non-parametric Kaplan-Meier estimate will be used to estimate the EFS function at one year. After 20 patients have been enrolled, the design will include interim analyses for futility that could halt the trial if it seems likely that the drug combination does not have sufficient clinical activity.

The sample size of 60 and the study design operating characteristics assume a three-year recruitment period with an additional follow-up of one year. Based on a study of high dose cyclophosphamide and rituximab without stem cell transplantation at our institution [2], the one and three-year EFS for low grade B cell lymphomas was 67 and 49% respectively. The simulation below demonstrates how the operating characteristics of the design varies when the uncertainty of the one-year EFS is characterized with the prior: beta(3,2). This implies that our prior guess at one-year EFS for these patients is 60%, and there is 90% probability that the EFS at 12 months is between 25% and 90%.

We have designed this study to stop early only if it appears that this treatment is associated with a lower one-year EFS than 50%. Specifically, the stopping rule will hold enrollment if the posterior probability of one-year EFS being less than 50% is 70% or higher. Simulations were carried out with exponential survival and staggered patient entry. We assumed, on average, 2 patients would enter the study per month. Interim analyses began once 20 patients entered the study and occurred after groups of 10 patients thereafter, up to a maximum of 60 patients. The interim analysis estimates of one-year EFS are based on analyses with an underlying Dirichlet process prior. We approximated the posterior distribution, which is actually a mixture of Beta distributions, the mixture depending on the amount of censoring, with a single Beta distribution. The parameters of this posterior Beta distribution are based on the number of failures and the effective sample size at 12 months, combined with the parameters of the prior. The following tables summarize the operating characteristics under various scenarios for the underlying exponential EFS, based on 1000 simulations. The 95% posterior intervals are the quantiles of

the simulated one-year EFS corresponding to probabilities of .025 and .957. The interpretation is that the posterior probability that the estimate of one-year PFS lies in this interval is 95%.

Prior is beta(3,2) : Mean is 0.60

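### Three-year EFS in a five-category cohort is tested against 49%, a low-grade benchmark, so the 5% error level against no added benefit is not assured

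*Combined protocol and SAP*

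**What the plan says.** The analysis of secondary objectives in section 6.0 contains one efficacy comparison with a stated null and alpha: "The three-year EFS will be compared to the null EFS of 49% with a Z-score and a one-sided alpha level of 0.05". The futility part of the same section gives the source of the 49%: in the institution's series of high-dose cyclophosphamide with rituximab, "the one and three-year EFS for low grade B cell lymphomas was 67 and 49% respectively".

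Section 1.2 reports that series of 81 adults by histology. For the 42 low-grade patients, 17% of whom had transformed lymphoma: "The EFS for low grade B cell patients at 3 and 5 years was 49% and 40"%. For the 39 mantle cell patients: "The 3 and 5 year EFS for MCL patients was 57% and 39"%. For the first 25 patients of a separate relapsed Hodgkin trial with another regimen: "actuarial event-free survival is 79% at 1 year and 63% at 2 and 3 years following high-dose cyclophosphamide".

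Section 3.2 admits five categories: mantle cell; other low-grade B-cell including SLL/CLL; transformed/DLBCL/PMBCL; gray zone; and Hodgkin. It sets no shares or caps. Section 3.2.1 gives 85% power for 49% against 69% with 60 patients, the whole planned enrolment. The analysis sentence does not say that the test is pooled, but this power statement implies it.

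Section 2.1 makes EFS specific to three groups (mantle cell, low-grade, high-grade). It does not say where Hodgkin, gray zone or transformed lymphoma belong. Section 6.0 restates the EFS objective and analyses it without histology.

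**The concern.** A single-arm comparison with a historical figure speaks to treatment benefit only if that figure is what the enrolled patients would have achieved without the study regimen. Here the figure comes from one of five enrolled categories, and the protocol's own results for two others are different. A rejection, or a failure to reject, would then partly reflect who was enrolled.

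Nothing else in section 6.0 covers this. The futility rule is about another quantity and threshold: "the stopping rule will hold enrollment if the posterior probability of one-year EFS being less than 50% is 70% or higher". The column headed "Prob H0 Rejected" sits in the table of simulations for that one-year monitoring, which varies one-year EFS and contains no histology mix.

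**Working it through.** **Inputs.** Null 49%, Z-score, one-sided 0.05 (section 6.0). n = 60, three-year recruitment, at least one year of follow-up (section 3.2.1). Three-year EFS without the study regimen: low-grade 49%, mantle cell 57%, Hodgkin 63% (section 1.2). The mixes below are assumptions, since the plan gives none.

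**Method.** EFS is taken as exponential with hazard λ = −ln(p)/3 and accrual as uniform. The Greenwood variance of the three-year Kaplan-Meier estimate is (p²/n) × ∫₀³ λ/[S(u)G(u)] du, where G(u) is the share of patients with follow-up beyond u. Follow-up runs from 1 to 4 years (one-year minimum), or is at least 3 years for all (full). Chance of rejecting = Φ[(p − 0.49)/SE(p) − 1.645].

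**1. The plan's own power.** At p = 0.69 with the one-year minimum, SE = 0.0727. Then 0.20/0.0727 − 1.645 = 1.10, and Φ = 87%. Simulating the Kaplan-Meier test gives 83%. The stated 85% is reproduced.

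**2. The level when the null is right.** At p = 0.49, SE = 0.080 (one-year minimum) or 0.0645 (full). The formula gives 5.0%; simulation gives 6% to 7%. The test is sound against 49% as a number.

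**3. No added benefit, benchmarks at face value.**

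| Mix | Expected EFS | One-year minimum | Full follow-up | Simulation or exact count |
|---|---|---|---|---|
| Half low-grade, half mantle cell | (49+57)/2 = 53% | Φ(0.04/0.0795 − 1.645) = 13% | Φ(0.04/0.0644 − 1.645) = 15% | 15%–17% |
| Equal thirds with Hodgkin | (49+57+63)/3 = 56.3% | Φ(0.073/0.0788 − 1.645) = 24% | Φ(0.073/0.0640 − 1.645) = 31% | 26%–33% |

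**4. Categories without a figure.** Take equal fifths and an assumed EFS of x for both transformed/DLBCL/PMBCL and gray zone. The mix equals 49% when (49 + 57 + 63 + 2x)/5 = 49, so x = 38%. With full follow-up the test rejects above 0.49 + 1.645 × √(0.49 × 0.51/60) = 0.596. The chance of rejecting with no benefit is then 1.6% at x = 30%, 5.0% at 38%, 17% at 49% and 39% at 60%. No value of x is given in the documents, so these figures show only that the answer lies on either side of 5% according to x.

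**5. Precision of the benchmarks.** Ignoring censoring, SE = √[p(1 − p)/n]: 7.7 points (n = 42), 7.9 (n = 39) and 9.7 (n = 25). Mantle cell minus low-grade is 8 points (95% CI −14 to +30). Hodgkin minus low-grade is 14 points (−10 to +38).

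**The case against.** The strongest reply is that the documents do not establish a histology difference. Both intervals in step 5 include zero, and five-year EFS in the institutional series is almost the same for low-grade (40%) and mantle cell (39%). The Hodgkin figure comes from another regimen and is timed from cyclophosphamide, whereas trial EFS runs from registration. All of this stands, and the rates in step 3 therefore depend on taking the benchmarks as exact. But imprecise benchmarks do not justify applying the low-grade figure to every category; they make any fixed null less secure.

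A reader might infer that the 5% level definitely fails, or that the test is biased towards a positive result. The documents support neither. The level holds if the mix-weighted expectation is 49%, and the test is conservative if it is lower. The two other figures given (57% and 63%) push upwards, but DLBCL/PMBCL and gray zone have no figure of their own and no planned share.

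It can also be said that a lighter correction would do: carry the histology-specific reporting of section 2.1 into section 6.0 and label 49% as a low-grade reference. That would cure the inconsistency, but a whole-cohort test against 49% would still have no clear meaning.

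**Conclusion.** The concern holds in this form: a single low-grade null is not justified for the mixed cohort, and the one-sided 5% level against no added benefit is not assured. With 60 patients and the protocol's benchmarks taken as exact, the chance of rejecting with no benefit is about 13% to 17% for half low-grade and half mantle cell, and about 24% to 33% for equal thirds with Hodgkin. It can be below 5% if the categories without a figure do clearly worse. The net direction and size cannot be determined from the documents. The rates assume exponential EFS, uniform accrual and the stated mixes.

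Separately, sections 2.1 and 6.0 disagree on whether EFS is analysed by histology, and three enrolled types have no stated group. EFS is secondary, so the change should be made, but it does not touch the primary safety analysis.

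**What to change.** In section 6.0, replace the comparison sentence with wording to this effect:

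> One- and three-year EFS will be estimated with 95% confidence intervals in each histology group. One formal comparison will be made, in low-grade and mantle cell patients combined: three-year EFS against the average of 49% and 57%, weighted by the numbers enrolled, by Z-score at one-sided alpha 0.05. It will be repeated with that null moved up and down by one benchmark standard error. Other groups will be reported descriptively.

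For an even split the null is 53%, with SE 0.5 × √(7.7² + 7.9²) = 5.5 points.

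Also:
- In section 2.1, assign every enrolled category, including Hodgkin, gray zone and transformed lymphoma, to a group, and make section 6.0 agree.
- Place transformed lymphoma consistently in the trial group and the benchmark. If it goes to the high-grade group, restate the 49% from the institutional series without those patients (17% of 42, about 7).
- State the time origin of the EFS figures for the 81-patient series in section 1.2.
- In section 3.2.1, restate the 85% for the null and number actually tested.

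The cost is wording and a new power statement; histology is already needed for eligibility. Fewer patients enter the formal test, and how many is not stated. Power for 53% against 73% with the one-year minimum is about 85% to 89% at n = 60, 73% to 76% at n = 40 and 65% at n = 30 (ranges span simulation and formula). If the target stays at 69%, the formula gives 71%, 56% and 46%.

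The fix does not remove benchmark uncertainty: averaged over it, the error for an even split is still about 9% to 11% at n = 60. Some case-mix difference within groups also remains; for example, SLL/CLL is eligible as low-grade, while the benchmark series was mainly follicular.
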